8.2 Visit 2 (V2, 7d)

- Record adverse events
- Record concomitant medications
- Physical examination
- Perform scale assessment (NIHSS, mRS, BI Index)
- Record combined vascular events
- Advise the subjects of the next follow-up date and inform them not to take the drug on the day of the follow-up

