9.1.2.1 Assessment and Procedures for Combined Vascular Events

After the occurrence of a combined vascular event, the study center must notify the sponsor within 24 hours upon receipt of the event notice. Vascular events will be reviewed by an independent Clinical Events Committee (CEC). Therefore, the endpoint event classification table will be included as part of the CRF. The investigator will record events in the aforementioned table and promptly submit supporting documents (admission and discharge records, medical records, death records, ECG, etc.). This information will be provided to the CEC for the determination of events.

The CEC is composed of a chairperson and 5–6 members. Each event will be independently reviewed by two members of the committee, and the conclusions will be submitted to the chairperson of the committee. If there is a disagreement between the two reviewing members or between the two reviewing members and the chairperson, when the number of dissenting events reaches a certain threshold, the entire committee will schedule a meeting to review the events.

9.2 Safety determination:

Adverse event assessment

• Clinical laboratory indicators:

Collect blood and urine samples in a fasting state (at least 10 hours of fasting, with water intake allowed but no consumption of coffee or tea) and send them to the laboratories of each center for testing according to uniform standards

Blood routine (hemoglobin, red blood cells, white blood cells, platelets), urine routine (urine protein, urine white blood cells, urine red blood cells), serum biochemistry (alanine aminotransferase, aspartate aminotransferase, alkaline phosphatase, total bilirubin, glutamine, urea nitrogen, creatinine, uric acid, blood glucose, total cholesterol, triglycerides, low-density lipoprotein, high-density lipoprotein), coagulation 4-item

12-lead ECG

Physical examination:

Comprehensive physical examination: General condition (including height, weight), vital signs (including blood pressure, pulse rate), skin (including hair and nails), eyes, ears, nose, and throat, neck/thyroid, chest/lungs, cardiovascular system, abdomen/gastrointestinal system, reproductive-urinary system (optional), nervous system, lymphatic system, and musculoskeletal system;

Simplified physical examination: General condition (including weight), vital signs (including blood pressure, pulse rate), chest/lungs, cardiovascular system

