The primary indicator will be assessed using a superiority test, testing the following hypothesis:

$$H_0: \pi_{Test\ group} - \pi_{Control\ group} \le 0$$

$$H_1: \pi_{Test\ group} - \pi_{Control\ group} > 0$$

$$\alpha = 0.025 (One - sided)$$

If the H_0 is rejected at the significance α level, or if the lower limit of the 95% CI for the difference in retention rates between the two groups is greater than 0, it can be considered that the treatment group is superior to the control group.

Other secondary indicators will be compared using the same statistical method as the primary indicator.

12.2.4. Safety evaluation:

Describe the number and proportion of subjects with normal values before treatment and abnormal values after treatment for both the treatment group and the control group separately. Describe adverse events using the number of cases, the number of subjects, and the incidence rate. Conduct inter-group significance tests will be conducted on the incidence rate. Additionally, provide a detailed description of the specific manifestations, severity, and the relationship with the drug for all adverse events observed in each group. Provide a cross-tabular description of the changes in laboratory indicators before and after the treatment. Compare vital sign indicators before and after the treatment.

13 Data Management

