Routine ECG should be performed within 24 h after ischemic stroke. Cardiac monitoring may be necessary to detect cardiac abnormalities early for appropriate management. Avoid or use drugs that increase the burden on the heart with caution.

- (iii) Temperature Control
- (1) Patients with elevated body temperature should have the cause of fever identified. If there is an infection, antibiotic therapy should be administered. (2) Patients with a body temperature >38°C should be given antipyretic measures.
- (iv) Blood Pressure Control
- 1. Hypertension: Approximately 70% of ischemic stroke patients experience blood pressure increased in the acute phase, mainly including pain, nausea and vomiting, increased intracranial pressure, confusion, anxiety, post-stroke stress state, pre-existing hypertension. In

the majority of patients, blood pressure spontaneously decreases within 24 h after a stroke. In patients with stable conditions and without intracranial hypertension or other serious complications, the blood pressure level after 24 h can essentially reflect their pre-illness level. Currently, there is a lack of reliable study evidence regarding whether blood pressure should be immediately lowered in the early stages after a stroke, what is the target values for blood pressure reduction, when to resume the original antihypertensive drugs post-stroke, and the choice of antihypertensive drugs. Domestic studies indicate that about 14% of patients have a systolic blood pressure ≥220 mmHg (1 mmHg = 0.133 kPa), and 56% have a diastolic blood pressure ≥120 mmHg upon admission.

2. Hypotension: Possible causes of hypotension in stroke patients include aortic dissection, decreased blood volume, and reduced cardiac output. The cause should be actively investigated, and appropriate treatment should be administered.

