Recommendation: (1) For candidates preparing for thrombolysis, the systolic blood pressure should be maintained at <180 mmHg and the diastolic blood pressure at <100 mmHg. (2) Patients with blood pressure increased within 24 h after ischemic stroke should be handled with caution. Anxiety, pain, nausea, vomiting, and increased intracranial pressure should be managed before addressing other issues. In cases of sustained increase in blood pressure, with systolic blood pressure ≥200 mmHg or diastolic blood pressure ≥110 mmHg, or in the presence of severe heart failure, aortic dissection, or hypertensive encephalopathy, antihypertensive treatment may be administered with caution. Blood pressure changes should be closely monitored, and if necessary, short-acting intravenous medications (such as labetalol, and nicardipine) can be used. It is preferable to use a microinfusion pump to avoid excessive lowering of blood pressure. (3) For individuals with a history of hypertension who are currently taking antihypertensive drugs, if the condition is stable, resumption of antihypertensive drug can commence 24 h after the stroke. (4) Patients with hypotension after a stroke should actively identify and address the underlying causes. If necessary, volume expansion and blood pressure support measures can be implemented.

(v) Blood Glucose Control

- 1. Hyperglycemia: About 40% of patients experience post-stroke hyperglycemia, which is associated with an unfavorable prognosis. It is currently recognized that control of post-stroke hyperglycemia is advisable, but there are only a few RCTs available on the specific measures and target blood glucose levels to be employed. No final conclusion has been reached yet.
- 2. Hypoglycemia: The incidence of hypoglycemia after a stroke is relatively low. Although there is a lack of clinical trials on its management, hypoglycemia can directly lead to cerebral ischemic injury and worsen edema, which is detrimental to the prognosis. Therefore, hypoglycemia should be corrected promptly.

Recommendation: (1) Administer insulin therapy when blood glucose exceeds 11.1 mmol/L. (2) Administer 10% to 20% glucose orally or by injection when blood glucose is below 2.8 mmol/L.

(vi) Nutritional Support

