6.2.5 Safety analysis

Adverse events are described with case number, times and incidence of various adverse events, and $\chi 2$ test or Fisher's exact test is adopted for comparing the incidence between the two groups. At the same time, make a detailed list to describe the specific manifestation and extent of all adverse events and serious adverse events and their relation with drugs.

Statistically describe the vital signs at baseline and 90 days after treatment according to general principles, and make comparison between former and later times and inter-group comparison.

Make description of number of normal cases before treatment, number abnormal cases after treatment and their ratios in two groups, respectively, and $\chi 2$ test or Fisher's exact test is adopted for comparing the ratio between the two groups.

Make description of number of normal cases before treatment, number abnormal cases after treatment and their ratios in two groups, respectively, and $\chi 2$ test or Fisher's exact test is adopted for comparing the ratio between the two groups. Crosstab is adopted to describe the change of laboratory indexes before and after treatment for determining the clinical significance of these indexes.

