7.4.2 Physical examination

Table 7.4.2.1 Comparison of vital sign indexes between before and after treatment (SS) - systolic pressure (mmHg)

Item	Index	Treatment group	Control group
	N(Missing)		-
Systolic pressure at baseline (mmHg)	Mean(SD)		
	Median		
	Q1,Q3		
	Min, Max		
	Statistics		
	P value		
	N(Missing)		
Systolic pressure at 90 days after treatment (mmHg)	Mean(SD)		
E ,	Median		
	Q1,Q3		
	Min, Max		
	Statistics		
	P value		
	N(Missing)		
Changes of systolic pressure at 90 day			
after treatment comparing with that at			
baseline			
	Median		
	Q1,Q3		
	Min,Max		
	Statistics		
	P value		
	95%CI		
	Statistics		
	P value		

 $Table \ 7.4.2.2 \ Comparison \ of \ vital \ sign \ indexes \ between \ before \ and \ after \ treatment \ (SS) \ - \ diastolic \ pressure \ (mmHg)$

Table 7.4.2.3 Comparison of vital sign indexes between before and after treatment (SS) – heart rate (times/minute)

The same as above

Table 7.4.2.4 Comparison of vital sign indexes between before and after treatment (SS) – pulse (times/minute)

The same as above

Table 7.4.2.5 Comparison of vital sign indexes between before and after treatment (SS) – body temperature ($^{\circ}$ C)

The same as above

Table 7.4.2.6 Numbers and percentages of normal cases before physical examination and abnormal cases after physical examination (SS)

	Treatment group	Control group	
Item	Case number Percentage	Case number Percentage	P value
General condition			
Skin and superficial lymph nodes			
Head and neck			
Heart			
Lung			
Abdomen			
Nervous system			
Urogenital system			
Spine and four limbs			
Others			

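### Vital signs are compared between arms only at baseline and Day 90, and the protocol names only a before/after comparison, so a transient early blood pressure difference could be absent from the safety tables

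*Combined protocol and SAP*

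**What the plan says.** **Protocol.** The safety evaluation in section 12.2.4 has one sentence on vital signs: "Compare vital sign indicators before and after the treatment". It names no comparison between arms for them, although the same paragraph plans a between-group test of adverse event incidence.

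**SAP.** Section 6.2.5 goes further. It fixes the time points, "Statistically describe the vital signs at baseline and 90 days after treatment according to general principles", and then says to "make comparison between former and later times and inter-group comparison". The shell for systolic pressure, Table 7.4.2.1, puts the arms side by side at baseline, at Day 90 and for the change, with test statistics, P values and a 95% CI. Tables 7.4.2.2 to 7.4.2.5 cover diastolic pressure, heart rate, pulse and temperature. None has a Day-7 or discharge block.

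**Measurement.** Protocol 8.2 (Day 7) and 8.3 (discharge) each list "Physical examination". Protocol 9.2 defines a full and a reduced form of that examination, and even the reduced form covers blood pressure and pulse: "Simplified physical examination: General condition (including weight), vital signs (including blood pressure, pulse rate), chest/lungs, cardiovascular system". Protocol 4.1 moves the discharge visit to Day 21 for stays longer than 21 days.

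**Missing data.** SAP 6.1.3 does not carry safety values forward.

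**Background course.** Appendix 7 says that in "the majority of patients, blood pressure spontaneously decreases within 24 h after a stroke". For stable patients already on treatment for hypertension, it says that "resumption of antihypertensive drug can commence 24 h after the stroke".

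**The concern.** A before/after change within one arm mixes three things: any drug effect, recovery from the acute stroke, and changes in background antihypertensive treatment, which protocol 6.2.3 allows throughout. Only a contrast between randomized arms isolates the first. The protocol names only the uninformative comparison. The SAP names both and does not say which one carries the safety conclusion.

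The SAP's contrast between arms rests on one post-baseline visit, three months after randomization. The readings closest to the start of treatment, at Day 7 and discharge, enter no planned comparison. At stake is whether the vital-sign tables can show an early difference that has faded or been treated away by Day 90, or one among patients who never reach the Day-90 reading.

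**Working it through.** **Step 1. The plan's own figure.** The only design calculation is for the primary endpoint (protocol 4.2, SAP 4.4): 40% v 47%, two-sided α = 0.05, power 80%.

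n = [1.960·√(2·0.435·0.565) + 0.842·√(0.40·0.60 + 0.47·0.53)]² / 0.07² = (1.374 + 0.589)² / 0.0049, which rounds up to 787 per arm.

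With the 20% allowance, 787/0.8 = 984 per arm, or 1,968 in total. Both figures reproduce. They say nothing about blood pressure but supply the numbers per arm used below.

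**Step 2. Visits against analyses.**

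| Visit | Blood pressure and pulse due | Arms compared in a vital-sign table |
|---|---|---|
| Baseline | yes | yes |
| Day 7 | yes (8.2 with 9.2) | no |
| Discharge/Day 21 | yes (8.3 with 9.2) | no |
| Day 90 | yes | yes |

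The SAP already tabulates mRS at 7 days, discharge and 90 days (Table 7.3.6.1), so the layout exists.

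**Step 3. What a within-arm test shows with no drug effect.** The documents give neither the size of the fall nor its SD. Assume a background systolic fall of 5 to 20 mmHg and an SD of change of 15 to 25 mmHg. With √787 = 28.05, t = fall/(SD/28.05):
- 5/(25/28.05) = 5.6
- 10/(20/28.05) = 14.0
- 20/(15/28.05) = 37.4

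With a fall of only 2 mmHg, P < 0.05 still occurs in 96%, 80% or 61% of trials for an SD of 15, 20 or 25.

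Now suppose the drug blunts the fall by 3 mmHg (7 v 10, SD 20). Both arms still show clear falls: t = 7/(20/28.05) = 9.8 and t = 14.0.

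**Step 4. What a between-arm test shows.** A fall common to both arms cancels.
- For the same 3 mmHg: z = 3/(20·√(2/787)) = 3/1.008 = 2.98.
- 95% half-width: 1.96 × 1.008 = 1.98 mmHg.
- Difference detectable with 80% power, (1.960 + 0.842)·SD·√(2/787): 2.1, 2.8 and 3.5 mmHg for an SD of 15, 20 and 25.

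The same contrast at Day 7 or discharge would be about as sensitive if the readings are complete. If the true difference has returned to zero by Day 90, the planned comparison there reaches P ≤ 0.05 only at its 5% false-positive rate.

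**Step 5. Patients without a Day-90 reading.** The allowance implies up to 984 − 787 = 197 dropouts per arm. Any who lack a Day-90 reading contribute nothing to the vital-sign change, because nothing is carried forward. This is a ceiling, not a forecast: protocol 5.3 asks for a final assessment at withdrawal, and 6.1.6.3 asks patients who stop the drug to complete the 3-month follow-up.

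**The case against.** The best reply is that the SAP already does the essential thing. It plans a comparison between arms with a 95% CI at Day 90, next to the before/after values in the same table. A reader of protocol 12.2.4 might infer that blood pressure is tested only within each arm; SAP 6.2.5 shows that it is not. The large t values in Step 3 show only that within-arm P values are uninformative, and no section says the safety conclusion rests on them.

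A reader might also infer that any early drug effect would be missed. That is too strong. An effect lasting to Day 90 is covered. An early effect reported as an adverse event enters the between-arm comparison of incidence in SAP 6.2.5.

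Nor does Appendix 7 prove a large fall from baseline in both arms. It places the fall in the first 24 h and adds that, in stable patients without serious complications, later levels largely match those before the illness. Enrollment runs to 72 h after onset (protocol 5.1), so many baselines may follow the fall. Its sentence on resuming treatment is permissive and limited to stable, previously treated patients.

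Finally, the Day-7 cell for physical examination cannot be read reliably in either flowchart as reproduced, so the Day-7 reading rests on the visit text in protocol 8.2.

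All of this stands and narrows the point. It leaves two things untouched: protocol and SAP name different vital-sign analyses, and two scheduled sets of readings enter no comparison between arms.

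**Conclusion.** The point holds in a limited form. Protocol 12.2.4 names a comparison that cannot isolate a drug effect. The SAP supplies the right kind of comparison, but at one post-baseline visit only. The gap is specific: a difference that is gone by Day 90, or that occurs in patients with no Day-90 reading, and that is not reported as an adverse event.

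Within that gap the unused data are worth having. With 787 per arm and an SD of change of 20 mmHg, each early visit would estimate the between-arm difference to within about 2 mmHg. The blood pressure falls and SDs are assumptions, and precision would be lower with incomplete readings. This concerns the completeness and alignment of a safety display. It does not show that blood pressure safety is untested or that a harmful effect would go undetected.

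**What to change.** - **Protocol 12.2.4 and SAP 6.2.5:** use the same wording in both. Name the between-arm comparison as the basis for the vital-sign safety conclusion, and describe before/after values without giving them inferential weight.
- **SAP Tables 7.4.2.1 to 7.4.2.5:** for each vital sign recorded at those visits, add rows for Day 7 and discharge/Day 21 with the between-arm difference and 95% CI, alongside Day 90. Label which statistic is within-arm and which is between-arm.
- **Method:** specify an independent-samples comparison or, preferably, one adjusted for the baseline value. The only parametric test in the general methods (protocol 12.2, SAP 6.2.1) is a paired t-test, which does not suit two independent arms. The rank-sum test also listed there does suit them, but does not by itself give a mean difference with a CI.
- **Day 7:** confirm that the flowcharts agree with protocol 8.2 on the physical examination.

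The cost is wording and a few table rows, with no visits or procedures beyond those in the visit text. The downside is more safety comparisons, which should be read descriptively.

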Abbreviations	Interpretation
AE	(Adverse Event)
ALT	Alanine aminotransferase
AST	Aspartate aminotransferase
BUN	Urea nitrogen
CI	(Confidence Interval)
Cm	Centimeter
CMH	Cochran-Mantel-Haenszel Cochran-Mantel-Haenszel test
Cr	Creatinine
CRF	Case report form
CRO	Contract research organization
DRQ	DRQ
F	F-statistics (results of covariance analysis)
FAS	(Full Analysis Set)
GCP	Good Clinical Practice
ITT	Intentionality (population)
LOCF	(Last Observation Carried Forward)
Max	Maximum value
Mean	Mean
Median	Median
Min	Minimal value
P	P value
Power	Power of test
PP	Per-protocol (population)
PPS	Per-protocol Set
SAE	Serious Adverse Event
SD	Standard Deviation
SOP	Standard operating procedure
SS	Safety set

2. Study title

A randomized, double-blind, placebo controlled evaluation, multicenter clinical study of Tongxinluo Capsule in ischemic stroke patients

3. Study objectives

The primary objective of this study: In comparison with placebo, to evaluate the improvement of self-help ability of patient's daily living after early application of Tongxinluo Capsule with treating ischemic stroke (within 72 hours after onset) for 90 days.

The secondary objective of this study: To investigate the improvement of neurologic impairment and self-help ability of patient's daily living, differences of disability rate, incidence of combined vascular events and incidence of ischemic cerebrovascular diseases, and safety of medication between placebo and early application of Tongxinluo Capsule with treating ischemic stroke (within 72 hours after onset) for 90 days. To evaluate the safety and effectiveness of Tongxinluo Capsule at different etiological typing and randomized times, and in different imaging subgroup analyses and more exploratory analyses.

4. Study design

4.1 Overall design and summary of study preparation

4.1.1 Overall design

This is a randomized, double-blind, placebo-controlled evaluation, multicenter clinical study in ischemic stroke patients.

4.1.2 Overall arrangement

All patients are randomly divided into the treatment group and control group at a ratio of 1:1. The patient receives study drug on the basis of current routine basic therapy.

Treatment group: Basic treatment + Tongxinluo Capsules (4 capsules per time, tid, oral administration)

Control group: Basic treatment + Tongxinluo Placebo Capsules (4 capsules per time, tid, oral administration)

Other traditional Chinese medicine or Chinese patent medicine (the traditional Chinese medicine having similar functional components with Tongxinluo Capsule) is not allowed to take during treatment period.

Follow-up should be made on the 7th day, discharge day (if the hospital stay is longer than 21 days, follow-up should be made on the 21th day) and 90th day after randomization, in order to make effective and safety evaluation until the end of study.

4.1.3 Trial flow chart

Study phase	Screening/ random grouping	Double-bline	Double-blind treatment stage			
Visit	1	2	3	4	5	
Number of days	3 days ago to day 0	Day 7±2	At the discharge day	Day 90±7		
Basic information						
Informed consent	•					
General data	•					
Medical history	•					
Physical		_			0	
examination	•		•	•		
Treatment						
Inclusion/ exclusion						
criteria						
Random allocation	•					
Distributing study	•					

drugs					
Record drug					
combination	•	•	•	•	
Drug recovery and			_	_	
counting			•	•	
Determination on			_	_	
compliance			•	•	
Completion				•	
Inclusion index					
CT or MRI	•		0	•	
Pregnancy test	•				
Safety index					
Blood routine test	•		0	•	0
Routine urine test	•		0	•	0
Biochemical test	•		0	•	0
Four items of			0	•	0
coagulation	•			•	
12-led ECG	•		0	•	0
Evaluation on AE		•	•	•	0
Efficacy index					
Modified Rankin					
scale	•				
NIHSS score	•	•	•	•	
BI index score	•	•	•	•	
		•	•	•	
Check					
Check by					
researchers					
Check by					
supervisors	•	,	•		
Check by head of					
sub-center					Ĭ

Note: Inclusion index CT or MRI*: if the patient has taken head CT or MRI in the clinical study unit within 72 hours before grouping, it is not necessary to take examination again, and the report or relevant copies can be attached in case history. MRI sequence examination (T1+T2+DWI+FLAIR+MRA+T2*) should be taken in the centre participating in imaging subgroups at baseline and last follow-up, baseline examination can be taken before or 3 days after randomization.

At discharge day*: If the hospital stay is longer than 21 days, the follow-up can be made on day 21.

Follow-up*: When there are persistent adverse events or laboratory abnormality or abnormal vital signs with clinical significance at the end of treatment, the researchers should take follow-up to obtain the measurement value, and the follow-up can be made by various means according to the specific condition, or by phone.

